2.2 Amgen Investigational Product Background

Recycling of the hepatic cell surface LDL receptor (LDLR) plays a critical role in the maintenance of cellular and whole body cholesterol balance by regulating plasma LDL-C levels. Recently it has been shown that Proprotein convertase subtilisin/kexin type 9 (PCSK9) plays an important role in the recycling and regulation of LDLR ([Horton et al, 2007](#); [Brown and Goldstein, 2006](#)). PCSK9 is a member of the subtilisin family of serine proteases and is expressed predominantly in the liver, kidney, and intestine ([Zaid et al, 2008](#)). Following secretion, it causes post-translational downregulation of hepatic cell surface LDLR by a mechanism that involves direct binding to the LDLR. Downregulation of hepatic LDLR in turn leads to increased levels of circulating LDL-C. Thus PCSK9 may represent a target for inhibition by novel therapeutics in the setting of dyslipidemia. The rationale for such an approach is available from studies in preclinical models, and from human genetic data that provide strong validation for the role of PCSK9 in modulating LDL-C levels and the incidence of CHD in man. These human studies have identified gain-of-function mutations in the PCSK9 gene that are associated with elevated serum LDL-C levels (> 300 mg/dL [approximately 7.8 mmol/L]) and premature CHD ([Abifadel et al, 2003](#)); and loss-of-function (LOF) mutations that are associated with low serum LDL-C levels (\leq 100 mg/dL [approximately 2.6 mmol/L]) ([Cohen et al, 2005](#)). Strikingly, subjects with

heterozygous LOF mutations exhibit lower serum PCSK9 levels and as much as 88% reduction in the incidence of CHD over a 15-year period compared with noncarriers of the mutations (Cohen et al, 2006). Moreover, despite complete loss of PCSK9 and associated very low serum LDL-C levels (< 20 mg/dL [approximately 0.5 mmol/L]), the 2 subjects who have been identified with compound heterozygote LOF mutations appear healthy (Hooper et al, 2007; Zhao et al, 2006).

Evolocumab is a fully human monoclonal immunoglobulin (Ig) G2 that binds specifically to human PCSK9 and prevents the interaction of PCSK9 with LDLR. Details of the biochemistry, nonclinical pharmacology, nonclinical pharmacokinetics (PK), and nonclinical toxicology with evolocumab are contained in the [Investigator's Brochure, 2016](#). Evolocumab binds to human, monkey, and hamster PCSK9 with high affinity ($K_d < 100$ pM). Evolocumab caused a dose-dependent inhibition of PCSK9 binding to the LDLR and of PCSK9-mediated reduction in low-density lipoprotein (LDL) uptake in HepG2 cells (human hepatocellular carcinoma cell line) in culture. In cynomolgus monkeys and in hamsters, in vivo administration of evolocumab resulted in reduced serum lipoprotein cholesterol levels in a dose-dependent manner. Based on a comprehensive package of PK, pharmacodynamics (PD), and toxicology studies ([Investigator's Brochure, 2016](#)), a program to develop evolocumab as a treatment for dyslipidemia was initiated.

Evolocumab binds to human, monkey, and hamster PCSK9 with high affinity ($K_d < 100$ pM). Evolocumab caused a dose-dependent inhibition of PCSK9 binding to the LDLR and of PCSK9-mediated reduction in low-density lipoprotein (LDL) uptake in HepG2 cells (human hepatocellular carcinoma cell line) in culture. In cynomolgus monkeys and in hamsters, in vivo administration of evolocumab resulted in reduced serum lipoprotein cholesterol levels in a dose-dependent manner. Based on a comprehensive package of PK, pharmacodynamics (PD), and toxicology studies ([Investigator's Brochure, 2016](#)), a program to develop evolocumab as a treatment for dyslipidemia was initiated.

2.3 Non-Amgen Medicinal Product Background

Ezetimibe 10mg tablets will be provided during study participation. Ezetimibe will be over-encapsulated to maintain blinding.

Ezetimibe is in a class of lipid-lowering compounds that selectively inhibits the intestinal absorption of cholesterol and related phytosterols. Ezetimibe is approved in Japan for treatment of hypercholesterolemia, familial hypercholesterolemia, and homozygous

sitosterolemia. For patients with homozygous familial hypercholesterolemia, ezetimibe should be used as an adjunct to HMG-CoA reductase inhibitor and other lipid-lowering non-pharmacological treatments (eg, LDL apheresis) or when such treatments are unavailable.

In the double blind placebo-controlled study of 100 Japanese hypercholesterolemia patients described in the label with a treatment duration of 12 weeks, LDL-C, total cholesterol, TG were reduced by 18.1%, 12.8% and 2.2%, respectively. HDL-C was increased by 5.9%.

In the ezetimibe clinical studies of 504 Japanese patients described in the label, 18.8% of patients on ezetimibe reported adverse reactions. The most commonly reported adverse reactions were constipation (3.0%), erythema (2.4%), diarrhea (2.2%), abdominal pain (2.0%), abdominal distension (1.6%), and nausea and vomiting (1.6%).

Ezetimibe is contraindicated in the following circumstances: in combination with a statin in patients with severe liver dysfunction and in patients with a known hypersensitivity to ezetimibe.

The recommended dose of ezetimibe is 10 mg once daily, administered after meal.

2.4 Rationale

There is an established unmet medical need in Japan for patients with hypercholesterolemia who experience muscle-related side effects when using statins. Amgen is therefore seeking an indication for the use of evolocumab alone or in combination with a statin or other lipid-lowering therapies in patients with hypercholesterolemia who are statin-intolerant or unable to tolerate an effective dose of a statin.

Subjects on low or atypical statin therapy must be on a stable dose for at least 4 weeks prior to screening and throughout the blinded portion of the study; the dose cannot be adjusted during screening and for the duration of the study.

This design provides a scientifically rigorous study to show the superiority of evolocumab over ezetimibe in Japanese patients who are intolerant to statins. Identified patients will be randomized 2:2:1:1 to QM evolocumab + PO placebo **each day (QD), every 2 weeks (Q2W)** evolocumab + PO placebo QD, QM SC placebo + ezetimibe QD, or Q2W SC placebo + ezetimibe QD for a head to head comparison evolocumab versus ezetimibe.

Long term exposure data will be provided by a 9-month open label extension where all patients will receive evolocumab in the same SC regimen (QM or Q2W) they were randomized to on Day 1.

2.5 Clinical Hypotheses

The primary hypothesis is that evolocumab will be well tolerated and will result in greater reduction of LDL-C than ezetimibe, defined by the mean percent change from baseline at Weeks 10 and 12 and percent change from baseline at Week 12, in Japanese hypercholesterolemic subjects who are intolerant to statins or unable to tolerate an effective dose of a statin.

3. EXPERIMENTAL PLAN

3.1 Study Design

This is a phase 3, multicenter, double-blind, randomized, ezetimibe controlled, parallel group study for evolocumab in hypercholesterolemic Japanese subjects unable to tolerate an effective dose of a statin. Subjects who meet all inclusion/exclusion criteria will be randomized with an allocation ratio of 2:2:1:1 into 4 groups: QM 420 mg SC evolocumab + QD PO placebo, Q2W 140 mg SC evolocumab + QD PO placebo, QM SC placebo + QD 10 mg PO ezetimibe, Q2W SC placebo + QD 10 mg PO ezetimibe. Randomization will be stratified by screening LDL-C level and baseline statin use. Randomization should occur within 5 – 10 days of the screening LDL-C evaluation used to determine eligibility. **Subjects on low or atypical statin therapy must be on a stable dose for at least 4 weeks prior to the screening and throughout the blinded portion of the study; the dose cannot be adjusted during screening and for the duration of the study.**

For blinding purposes, every subject will receive investigational product (IP) SC and PO. Patients will be provided with evolocumab or placebo through the use of an autoinjector (AI) or Personal Injector. Depending on availability either a single Personal Injector or 3 autoinjectors will be provided for monthly dosing. A single AI will be used for Q2W dosing. Evolocumab and corresponding placebo will be administered at the study site or at appropriate non-clinic setting per [Table 1](#) (Schedule of Assessments). PO placebo will be available to match PO ezetimibe through over-encapsulation. The SC IP dose frequencies of Q2W and QM will not be blinded.

Following the Week 12 visit, all subjects will self-administer IP in the non-clinic setting; subjects will return to the clinical site at W24, W36, W48 and W52 for subsequent visits.

There will be an end of study phone call at W54 (**Q2W subjects only**) for any potential adverse events, serious adverse events, or adverse device effects.

Central laboratory results of the lipid panel, ApoA1, ApoB, lipoprotein(a), and high sensitivity C-reactive protein (hsCRP) will be blinded during double-blind treatment. Investigators will be provided lipid results starting at week 24 until the end of study for each subject. All lipid results from posttreatment to week 24 will remain blinded until the unblinding of the clinical database.

The study includes collection of biomarker samples, where approved by the institutional review board (IEC/IRB). Administration of PO IP (ezetimibe or placebo) will end with the week 12 visit for all subjects. Following the week 12 visit, subjects should be treated to standard of care in addition to receiving open label evolocumab.

Subjects will be encouraged to complete all planned visits regardless of their adherence to investigational product (IP) administration. Formal review of the accumulating blinded data by an independent Data Monitoring Committee (DMC) **will occur**.

The study endpoints are defined in [Section 10.1.1](#).

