- LDL-C response (LDL-C < 70 mg/dL [1.8 mmol/L])
- Percent change from baseline in total cholesterol
- Percent change from baseline in non-HDL-C
- Percent change from baseline in ApoB
- Percent change from baseline in the total cholesterol/HDL-C ratio
- Percent change from baseline in ApoB/ApoA1 ratio

Tier 2

- Percent change from baseline in Lp(a)
- Percent change from baseline in triglycerides
- Percent change from baseline in HDL-C
- Percent change from baseline in VLDL-C

Study Design: This is a phase 3, multicenter, double-blind, randomized, ezetimibe controlled, parallel group study for evolocumab in hypercholesterolemic Japanese subjects unable to tolerate an effective dose of a statin. Subjects who meet all inclusion/exclusion criteria will be randomized with an allocation ratio of 2:2:1:1 into 4 groups: evolocumab 420 mg SC QM + placebo PO QD, evolocumab 140 mg SC **every 2 weeks (Q2W)** + placebo PO QD, placebo QM SC + ezetimibe 10 mg PO QD, placebo SC Q2W + ezetimibe 10 mg PO QD. Randomization will be stratified by screening LDL-C level and baseline statin use. Randomization should occur within 5 – 10 days of the screening LDL-C evaluation used to determine eligibility. Subjects on low or atypical statin **therapy must be on a stable dose for at least 4 weeks prior to screening and throughout the blinded portion of the study; the dose cannot be adjusted during screening and for the duration of the study.**

To ensure tolerance of SC injections, patients will receive a 1-time placebo injection by AI/Pen prior to randomization.

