For blinding purposes, every subject will receive investigational product (IP) SC and PO. Subjects will be provided with evolocumab or placebo through the use of a prefilled autoinjector/pen (AI/Pen) or Personal Injector (also known as the automated mini-doser [AMD]). Depending on availability either a single Personal Injector will be provided for monthly dosing (QM) or QM evolocumab may be provided by the use of 3 autoinjectors. Evolocumab and corresponding placebo will be administered at the study site or at an appropriate non-clinic setting per protocol Table 1 (Schedule of Assessment). PO placebo will be available to match PO ezetimibe through over-encapsulation. The SC IP dose frequencies of Q2W and QM will not be blinded. Evolocumab SC, ezetimibe PO, and placebo SC and PO will be blinded. Central laboratory results of the lipid panel, ApoA1, ApoB, lipoprotein(a), and high sensitivity C-reactive protein (hsCRP) will be blinded during double-blind treatment. Investigators will be provided lipid results starting at week 24 until the end of study for each subject. All lipid results from posttreatment to week 24 will remain blinded until the unblinding of the clinical database.

Subjects will self-administer IP in the non-clinic setting and return to the clinical site at W24, W36, W48 and W52 for subsequent visits. There will be an end of study phone call at W54 (**Q2W subjects only**) for any potential adverse events/serious adverse events/**adverse device effects.**

The study includes collection of biomarker samples, where approved by the institutional review board (IEC/IRB). Administration of non-Amgen IP: PO IP (ezetimibe or placebo) will end with the week 12 visit for all subjects. Following the week 12 visit subjects should be treated to standard of care in addition to receiving Amgen IP: open label evolocumab.

Subjects will be encouraged to complete all planned visits regardless of their adherence to investigational product (IP) administration. The study includes a formal review of the accumulating blinded data by an independent Data Monitoring Committee (DMC).

Sample Size: Approximately 60 subjects (approximately 40 evolocumab subjects) will be randomized. A subject will be considered enrolled upon randomization.

Investigational Product(s) Dosage, Administration, Protocol-required Therapies, and Standard of Care:

Amgen Investigational Product Dosage and Administration

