Evolocumab will be administered using a spring-based prefilled autoinjector/pen (prefilled AI/Pen) or 3.5 mL Personal Injector.

Evolocumab will be administered at 1 of 2 regimens:

Evolocumab 140 mg SC Q2W (1 prefilled AI/Pen injection) or

Evolocumab 420 mg SC QM (3 prefilled AI/Pen injections or 1 Personal Injector injection)

Non Amgen Investigational Product Dosage and Administration: Ezetimibe 10 mg (and placebo) will be provided by Amgen (or designee) and will be taken by the subject PO QD. Placebo will be matching ezetimibe by over-encapsulation.

Amgen will not provide Standard of Care (SOC) medication for the open label period.

Summary of Subject Eligibility Criteria: Males and females, ≥ 20 to ≤ 80 years of age, **Japanese by self-identification**, are eligible for this study. Subject must have tried and failed at least 2 statins with failure to at least 1 of the statins at an average daily dose at or below the following doses due to intolerable myopathy, ie, myalgia (muscle pain, ache, or weakness without CK elevation), myositis (muscle symptoms with increased CK levels), or rhabdomyolysis (muscle symptoms with marked CK elevation). For subjects that developed rhabdomyolysis, defined as CK $> 10 \times$ ULN, failure of only 1 statin at any dose is acceptable.

- Atorvastatin 10 mg
- Fluvastatin 20 mg
- Pravastatin 10 mg
- Rosuvastatin 2.5 mg
- Simvastatin 5 mg
- Pitavastatin 1 mg
- For unlisted statins, the average daily dose should not exceed the lowest available recommended starting dose approved by the Japanese Ministry of Health, Labour and Welfare.

Symptoms must have resolved **or improved** when statin was discontinued or the dose was reduced. Depending on a subject's management category per 2012 JAS guideline (see [Appendix D](#)) subjects must meet criteria provided. Fasting triglycerides must be ≤ 400 mg/dL (4.5 mmol/L) as determined by the central laboratory analysis at screening.

Major exclusion criteria include, but are not limited to moderate to severe heart failure, uncontrolled cardiac arrhythmia, symptomatic coronary artery disease within the last 3 months, recently diagnosed or poorly controlled diabetes, hypertension or hyper/hypothyroidism, known active infection or major hematologic, renal, hepatic, metabolic, gastrointestinal or endocrine dysfunction, systemic steroid use, pregnancy or lactation, previous exposure to evolocumab or other PCSK9 inhibitor.

Statistical Considerations:

General Considerations

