4.1 Inclusion and Exclusion Criteria

4.1.1 Inclusion Criteria

- 101 Subject who has provided informed consent/assent prior to initiation of any study-specific activities/procedures
- 102 Male or female ≥ 20 to ≤ 80 years of age, **Japanese by self-identification**, at signing of informed consent
- 103 Subject who is not at LDL-C goal as evidenced by the 2012 JAS management category and the following LDL-C levels by central laboratory at screening:
- a) Fasting LDL-C ≥ 100 mg/dL (2.59 mmol/L) for subjects with diagnosed CHD or are CHD risk equivalent or
 - b) Fasting LDL-C ≥ 120 mg/dL (3.37 mmol/L) for subjects without diagnosed CHD or risk equivalent and Management Category III
 - c) Fasting LDL-C ≥ 140 mg/dL (4.14 mmol/L) for subjects without diagnosed CHD or risk equivalent and Management Category II
 - d) Fasting LDL-C ≥ 160 mg/dL (4.9 mmol/L) for subjects without diagnosed CHD or risk equivalent and Management Category I
- 104 Subject must have tried and failed at least 2 statins with failure to at least 1 of the statins at an average daily dose at or below the following doses due to intolerable myopathy, ie, myalgia (muscle pain, ache, or weakness without CK elevation), myositis (muscle symptoms with increased CK levels), or rhabdomyolysis (muscle symptoms with marked CK elevation). For subjects that developed rhabdomyolysis, defined as CK $> 10 \times$ ULN, failure of only 1 statin at any dose is acceptable. **Symptoms must have resolved or improved when statin was discontinued or the dose was reduced.**

- Atorvastatin 10 mg
- Fluvastatin 20 mg
- Pravastatin 10 mg
- Rosuvastatin 2.5 mg
- Simvastatin 5 mg
- Pitavastatin 1 mg
- For unlisted statins, the average daily dose should not exceed the lowest available **recommended** starting dose approved by the **Japanese Ministry of Health, Labour and Welfare**.

105 **Subjects taking bile-acid sequestering resins and/or stanol, stanol esters, low (lowest available recommended starting dose approved by the Japanese Ministry of Health, Labour and Welfare) or atypical dose of statin must be on a stable dose for at least 4 weeks prior to screening. No adjustments to statin (or other lipid lowering therapy) dose are allowed during screening and throughout study.**

EXCEPTION: if subject is on ezetimibe at start of screening it must be discontinued for ≥ 1 week before LDL-C screening

106 Fasting triglycerides ≤ 400 mg/dL (4.5 mmol/L) by central laboratory at screening

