6.4 Concomitant Therapy, Diet, and Exercise

Throughout the study, investigators may prescribe any concomitant medications or treatments deemed necessary to provide adequate supportive care except for those listed in [Section 6.7](#).

Subjects should maintain their current regimen of diet and exercise. Subjects will be required to refrain from unaccustomed intensive exercise (eg, heavy lifting or long runs) 48 hours prior to each visit.

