6.7 Excluded Treatments and/or Procedures During Study Period

The following treatments are not permitted during the study:

- Prescription lipid regulating medications (eg, non-study ezetimibe, or fibrates and derivatives)
- **However, the following agents are allowed:**
 - bile-acid sequestering resin
 - stanol and stanol esters
 - **Please note: subjects on a low (lowest available recommended starting dose approved by the Japanese Ministry of Health, Labour and Welfare) or atypical dose of statins may continue their current dose if the subject has taken it for at least 4 weeks prior to the screening; new statin initiations, and/or dose adjustments are not permitted during screening or the study itself.**
- Red yeast rice, niacin > 200 mg per day
- Any other drug that significantly affects lipid metabolism (eg, systemic cyclosporine, systemic steroids [IV, IM, or PO] (*Note: hormone replacement therapy is permitted, vitamin A derivatives and retinol derivatives for the treatment of dermatologic conditions [eg, Accutane]*). Vitamin A as part of a multivitamin preparation is permitted.

- Prescribed amphetamines, or amphetamine derivatives, and weight loss medications.

Should there be a clinical need to prescribe one of these treatments, the investigator should call the Amgen Medical Monitor to discuss.

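### Does telling sites to treat to standard of care after week 12 clash with the study-long limits on lipid drugs?

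*Protocol*

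**What the plan says.** **Standard of care after week 12.** Protocol Section 3.1 says: "Following the week 12 visit, subjects should be treated to standard of care in addition to receiving open label evolocumab". The synopsis has the same instruction ("Following the week 12 visit subjects should be treated to standard of care in addition to receiving Amgen IP: open label evolocumab"), and SAP Section 3.1 repeats it. The synopsis also says "Amgen will not provide Standard of Care (SOC) medication for the open label period", so some medication is expected to form part of that care. Neither document defines standard of care.

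**Limits on lipid drugs.** Protocol Section 6.7 opens with "The following treatments are not permitted during the study" and lists "Prescription lipid regulating medications (eg, non-study ezetimibe, or fibrates and derivatives". It then allows resins, stanols and an unchanged low or atypical statin dose, rules out starting a statin or changing its dose, and sends clinical need to the medical monitor. Inclusion criterion 105 adds: "No adjustments to statin (or other lipid lowering therapy) dose are allowed during screening and throughout study".

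**Statin stability.** The synopsis, Protocol Sections 2.4 and 3.1, and SAP Section 3.1 require a stable statin dose "throughout the blinded portion of the study; the dose cannot be adjusted during screening and for the duration of the study".

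**General concomitant therapy.** Protocol Section 6.4 says "Throughout the study, investigators may prescribe any concomitant medications or treatments deemed necessary to provide adequate supportive care except for those listed in" Section 6.7.

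**The concern.** The standard-of-care sentence comes straight after the statement that oral product stops at week 12, so it reads as advice on what to do next. In patients with hypercholesterolaemia, standard of care could well mean a lipid drug. Section 6.7 bars most prescription lipid drugs without mentioning the extension, and the standard-of-care sentence does not mention Section 6.7. The statin sentence names two periods, the blinded portion and the whole study, which could suggest that the rule relaxes at week 12.

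If sites read this differently, some subjects would have a lipid drug added or changed in the extension and others would not. The long-term LDL-C summaries in the final analysis would then describe evolocumab plus varying background therapy, and the variation would depend on the site.

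**Working it through.** The plan states no figure on this point, so the check is mainly a comparison of the passages.

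**1. Can the instructions be followed together?** Protocol Section 3.5.1 counts the nine-month extension as part of the 12 months of participation. Section 6.4 covers the whole study and makes Section 6.7 its exception. A general instruction to give standard of care can therefore be read within that exception. Resins, stanols, an unchanged low or atypical statin and all non-lipid care remain open, and the medical monitor handles exceptions. This is a reading of the text, not a view on what the clinical rule ought to be.

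**2. Do the two statin clauses conflict?** Clause A asks for a stable dose from four weeks before screening through the blinded portion. Clause B forbids adjustment during screening and for the rest of the study. From screening onward, meeting B guarantees meeting A. Clause A also carries the four-week requirement before screening, so it is not redundant. The clauses nest.

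**3. Which results could be touched?**

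| Result | Source | Exposed? |
|---|---|---|
| Co-primary, co-secondary and tertiary comparisons | SAP 10.1: treatment effect evaluated through the week 12 visit | No |
| Week 12 lipid value | SAP Appendix B: window closes at the earlier of day 91 and the first open-label dose | No practical route |
| Power and error control | SAP 3.2 and 10.1: rest on the comparisons above | No |
| Extension lipid summaries | SAP Table 2: by group, without inference | Yes, descriptively |

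**4. For how long?** Scheduled follow-up after week 12 is 52 − 12 = 40 weeks, or 40/52 = 77% of the study. Protocol Sections 3.1 and 7.2.5.3 release lipid results to investigators only from week 24, and Section 7.2 asks them not to test these analytes themselves before then. Changes guided by LDL-C are thus largely confined to 52 − 24 = 28 weeks, or 28/52 = 54%. Restarting an earlier drug without a lipid value remains possible from week 12.

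**5. Would a reader of the report see it?** SAP Section 10.6.6 tabulates lipid-regulating drugs at baseline and in each part of the study, and the incidence of changes in the extension.

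**6. What would a correction reach?** SAP Section 10.1 describes the primary analysis as completed, with a data cut-off of 02 November 2017. That analysis required every subject to have passed week 24 or left. A clarified rule could cover at most the last 28 weeks. As a protocol amendment it would need investigator agreement and ethics approval (Protocol Section 12.1) at about 40 sites (Section 3.2).

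**7. Would an extra summary that sets apart values after a lipid-drug change help?** Planned group sizes after the 5% allowance are 0.95 × 40 = 38 (pooled evolocumab), 0.95 × 20 = 19 (pooled ezetimibe, or one evolocumab regimen) and 0.95 × 10 = 9.5 (one ezetimibe regimen). If 10% changed therapy (an assumption; the documents give no rate), the cells would hold about 3.8, 1.9 and 1.0 subjects. The split would also select on response, since changes may follow high LDL-C, and it would be defined after unblinding.

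**The case for a change.** The best case for a change is that a workable inference is not a written rule. Neither Section 6.4 nor Section 6.7 mentions standard of care or the extension, and a site that thinks standard of care has been directed has no prompt to call the medical monitor. The guideline in Protocol Appendix D names resin, probucol and ezetimibe as options when statins cannot be given, whereas Section 6.7 allows resin and lists non-study ezetimibe as excluded. With about 40 sites for 60 subjects (60/40 = 1.5 per site), differences in reading become differences between subjects. Long-term efficacy is part of the purpose of the final analysis, and a clarifying sentence looks cheap.

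Much of this stands as a criticism of the drafting. The link between the passages is unwritten, and the guideline text could draw a site in either direction. But differing practice is a possibility, not something the documents show. It could reach only descriptive summaries whose lipid-drug changes are reported separately. The correction is also less cheap than it looks: besides the approvals, a rule restated partway through the extension could make earlier and later extension data differ.

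One argument for leaving the plan alone should not be used: that any shift would be smaller than the sampling error of a group mean. A systematic shift and random error are different quantities, and no inference is planned in the extension.

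**Conclusion.** No change to the plan follows. The passages are loosely drafted and lack a cross-reference, but they can be followed together, and the two statin clauses agree. The effect on the co-primary comparison, power and familywise error is nil. The remaining effect is possible variation in background lipid therapy in the descriptive extension summaries, mainly over the 28 weeks after lipid results are released. Its size cannot be derived, because the documents give neither the share of subjects who would start or change a drug nor which drug it would be. The planned tabulation of lipid-drug use and changes lets a reader judge it.

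This conclusion assumes that Section 6.4 governs the extension as its wording says, that lipid blinding holds to week 24, and that the extension analyses stay descriptive. If extension data were later used for inference, or the protocol were reopened for another reason, the standard-of-care sentence, Section 6.7 and criterion 105 should be reconciled, with the clinical rule left to the sponsor.
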